### 1.2. Timings of Analyses

The primary analysis for the primary efficacy endpoint of overall response rate (ORR) for the follicular lymphoma (FL) cohort (i.e., Primary Analysis for FL) will be triggered after all 91 subjects in the Primary Efficacy Population in FL (PEP FL) enrolled in the study (except those who discontinue early) have been followed for at least 6 months from the start of study drug.

The final analysis for DOR for follicular lymphoma (FL) to support the New Drug Application (NDA) initial filing for FL (i.e., NDA Analysis for FL) will be triggered after most responders in the Primary Efficacy Population have a minimum of 12 months of follow-up from first response.

The primary analysis for the primary efficacy endpoint of ORR for marginal zone lymphoma (MZL) (i.e., Primary Analysis for MZL) will be triggered after all subjects in the ITT MZL population enrolled in the study (except those who discontinue early) have been followed for at least 6 months from the start of study drug.

The final analysis for DOR for MZL to support the NDA filing for MZL (i.e., NDA Analysis for MZL) will be triggered after most responders in the ITT MZL population have a minimum of 12 months of DOR follow-up.

The final analysis includes all data collected through the time of the database lock. PK and Exposure-Response analyses will be performed by Nuventra, who will produce the analysis report.

An independent DSMB (Data Safety and Monitoring Board) will review descriptive summaries of accumulating safety, subject disposition, and limited efficacy data every 6 months. Further description of the DSMB analyses can be found in the DSMB charter.

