### **3.2.5. Time to Treatment Failure (TTF)**

Time to treatment failure is defined as time from the first dose of study drug to treatment failure. Treatment failure is defined as any treatment discontinuation due to PD, toxicity, or death.

Censoring rule for TTF:

- Subjects who are still alive and on treatment will be censored at the last disease assessment date indicating the absence of progression;
- Subjects who have treatment discontinued for reasons other than PD, AE, or death, will be censored at the treatment discontinuation date.

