### **3.3.3. Time to Occurrence of Adverse Event of Special Interests (AESIs)**

Time to occurrence of AESIs is defined as the time from first dose of study drug to first occurrence of an AESI.

Censoring rules for time to occurrence of AESIs:

- Subjects without AESI who are still on treatment will be censored at the data cutoff date;
- Subjects without AESI who discontinue from treatment will be censored at the treatment discontinuation date.

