**Table 4: Types of Analyses and Corresponding Populations for Planned Primary Analysis and NDA Analysis for FL**

Planned Analysis	Type of Analysis	Population	Analysis Set / Group
Primary Analysis for FL	Baseline disposition and demographics	ITT IS FL	ITT IS FL Total
	Primary endpoint ORR	PEP FL 	PEP FL
	Secondary endpoint DOR	PEP FL	DOR Primary Analysis Set for FL
	Selected Critical Secondary endpoints (PFS, OS)	PEP FL	PEP FL
	Selected Safety endpoints	Safety IS FL population	Safety IS FL Total
NDA Analysis for FL	Baseline disposition and demographics	ITT FL	PEP FL, ITT IS FL, ITT CS, ITT FL Total
	Primary endpoint ORR (Primary Analysis) and all secondary endpoints	PEP FL 	PEP FL
	Primary endpoint ORR (Supportive Analysis)	PEP FL 	PEP FL
	Primary endpoint ORR (Supportive Analysis)	ITT FL 	PEP FL, ITT IS FL, ITT CS, ITT FL Total
	Secondary endpoint DOR (Primary Analysis)	PEP FL	DOR Primary Analysis Set for FL
	Secondary endpoint DOR (Supportive Analysis)	ITT IS FL	DOR Supportive Analysis Set for FL
	Selected critical efficacy endpoints (PFS, OS, etc.)	ITT FL	PEP FL, ITT IS FL, ITT CS, ITT FL Total
Safety endpoints	Safety population	IS FL, IS MZL  , IS Total, CS	
Primary Analysis and NDA Analysis for MZL	Baseline disposition and demographics	ITT MZL	ITT MZL
	Primary endpoint ORR and all secondary endpoints (except DOR)	ITT MZL	ITT MZL
	Secondary endpoint DOR	ITT MZL	DOR Analysis Set for MZL
	Safety endpoints	Safety population	IS FL, IS MZL, IS Total, CS

 Primary analysis for ORR will include best response of PR and/or CR prior to first PD that is reported before the data cutoff date for FL Primary Analysis, among all patients in the Primary Efficacy Population in FL (PEP FL).

 Supportive analysis for ORR will include PR or CR achieved that is reported before the data cutoff date for NDA Analysis for FL, among all patients in the Primary Efficacy Population in FL.

 Supportive analysis for ORR will include PR or CR achieved that is reported before the data cutoff date for NDA Analysis for FL, among all patients in the ITT FL Population.

 Including MZL patients in the Safety Population who were dosed prior to the data cutoff date for the NDA Analysis for FL.

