### **7.2.5. Time to Treatment Failure (TTF)**

TTF is the time from the first dose of study drug to treatment failure (any treatment discontinuation due to PD, toxicity, or death). The analysis of TTF will be performed based on the assessment by IRRC and investigator, separately.

TTF will be summarized using Kaplan-Meier summary statistics for PEP FL and ITT MZL population. The median TTF with 95% CIs (Brookmeyer and Crowley method), number of events, number censored, and KM plot of proportion of subjects without treatment failure over time will be presented. TTF will be reported in months. Estimate and 95% CI for 1-year TTF rate, and reverse KM estimate median with 95% CI for follow-up time (months) will be summarized.

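### TTF censors on-treatment subjects at their last clean scan but still counts later failures, so the right-hand tail of the Kaplan-Meier TTF curve is biased downward

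*SAP*

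**What the plan says.** SAP 3.2.5 defines the event: "Treatment failure is defined as any treatment discontinuation due to PD, toxicity, or death". It then gives two censoring rules.

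- Subjects who are alive and still on drug "will be censored at the last disease assessment date indicating the absence of progression".
- Subjects who stop for another reason: "Subjects who have treatment discontinued for reasons other than PD, AE, or death, will be censored at the treatment discontinuation date".

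Neither rule limits failures to those seen by the last scan, and SAP 1.2 states: "The final analysis includes all data collected through the time of the database lock". SAP 7.2.5 reports the Kaplan-Meier median, the 1-year rate and the plot for PEP FL and ITT MZL.

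For time to first AESI, another event that can occur on any day, SAP 3.3.3 uses a different rule: "Subjects without AESI who are still on treatment will be censored at the data cutoff date". SAP 8.1 likewise runs exposure to the data cutoff for subjects still on study drug. Protocol 7.2.4 defines TTF without a censoring rule, so the last-scan rule comes from the SAP alone, and SAP section 10 gives no reason for it.

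**The concern.** Last-scan censoring suits PFS and DOR, where progression is seen only at scans and nothing is known after the last one. TTF is different. A subject on drug at the cutoff is known to be free of failure at the cutoff.

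Take two subjects with the same last clean scan. One then stops for toxicity and counts as an event on the stop date. The other stays on drug and is removed back at the scan. Whether follow-up after the scan is credited depends on whether the subject fails. Kaplan-Meier estimation assumes that censoring does not depend on the outcome in this way. The hazard after the last scans is overstated, and the later curve is too low. This arises even if nobody switches dosing schedule. At stake is the accuracy of a reported secondary endpoint.

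**Working it through.** **The plan's own figure.** The documents give no target, event count or expected rate for TTF, so there is nothing to reproduce.

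**Direction.** Take *n* subjects whose last clean scan before the cutoff is on day *s*, with the cutoff on day *c*. Suppose *d* of them fail between *s* and *c*.

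- Censoring at the cutoff: *n* at risk, *d* events; conditional survival (*n* − *d*)/*n* if all share the same cutoff day.
- SAP rule: the *n* − *d* survivors are removed at *s*. The *d* left at risk all fail, so this group contributes a conditional survival of 0.

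Subjects with longer follow-up dilute this, but its direction is always downward.

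**Length of the gap.** The imaging days are 61, 121, 182, 274, 365, 456, 547 and 730 (Protocol Appendix 1; SAP Table 1). Intervals run from 121 − 61 = 60 days, through 274 − 182 = 92, to 730 − 547 = 183. The gap between last scan and cutoff lies between zero and the interval in force. Its simulated mean was about 1.5 to 2.7 months.

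**Simulation inputs.**

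- Failure rates scaled from the Phase 1b IS group (Protocol 1.6.2.3): 43 subjects, median follow-up 155 days, 9 stops for PD, 2 for AE, 2 for other reasons. Taking 43 × 155 / 30.4375 ≈ 219 person-months as a rough exposure gives 9/219 = 0.041 per month for PD and 2/219 = 0.009 for AE.
- Assumed, not in the documents: accrual over 12 to 24 months, toxicity hazards up to 0.04 per month, in some runs an 18-month median time to PD, and a lag of 0, 0–14 or 0–40 days from PD scan to stopping.
- PD is found only at scans; toxicity and death occur on any day. Switching from IS to CS is not modelled.

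For each data set, the curve under the SAP rule was compared with the curve that censors ongoing subjects at the cutoff. Where compared with the true event-free share, the cutoff rule was within about 0.2 points at 1 year.

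**Results (shortfall under the SAP rule).**

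| Minimum follow-up | Quantity | N = 91 trials, lag 0 or 0–14 days | Large-sample runs, lag 0–40 days |
|---|---|---|---|
| 14 months | 1-year rate | 0.0 points | 0.0–0.1 points |
| 14 months | 18-month rate | 0.2–2.5 points | 0.8–2.4 points |
| 14 months | 24-month rate | not run | 2.0–12.3 points |
| 14 months | median | not run | 0–0.3 months |
| 6 months | 1-year rate | 0.4–5.1 points | 1.2–4.5 points |
| 6 months | median | not run | 0.1–2.9 months |

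The N = 91 trials used 12-month accrual at 14 months' minimum follow-up, and 12- or 18-month accrual at 6 months. The large-sample runs used 12 to 24 months.

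Example at the Phase 1b rates, 6-month minimum and 12-month accrual. With no lag, the true 1-year rate is 54.8%, the cutoff rule gives 54.8% and the SAP rule 54.2%. With a 0–14 day lag, the true rate is 61.8%, the cutoff rule gives 61.8% and the SAP rule 56.7%, a shortfall of 61.8 − 56.7 = 5.1 points.

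The wide 24-month range reflects accrual. With a 14-month minimum and 12-month accrual, the longest follow-up is 14 + 12 = 26 months, so few subjects reach 24 months and the bias is largest.

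**Which analyses report TTF.** SAP Table 4 lists ORR, DOR, PFS, OS and selected safety for the FL Primary Analysis; TTF is not named. TTF enters at the FL NDA Analysis, once most responders have 12 months from first response (SAP 1.2). For MZL, Table 4 puts ORR and every secondary endpoint other than DOR in both the Primary and the NDA Analysis, and SAP 1.2 triggers the Primary at 6 months. Protocol 5.1, 7.2 and 11.2.2 instead plan one final MZL analysis of ORR and DOR, at 12 months from first response or about 14 months from first dose.

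**Scale.** Ignoring censoring, the standard error of a rate near 55% is √(0.55 × 0.45/91) = 5.2 points for 91 FL subjects and √(0.55 × 0.45/32) = 8.8 points for 32 MZL subjects.

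**The case against.** The best reply is that the planned TTF numbers hardly move. At about 14 months' minimum follow-up, the median and 1-year rate are nearly unchanged, and any shift is small beside a standard error of 5 to 9 points. The 18- and 24-month rates are not planned TTF outputs; they only describe the tail of the plot. The bias is conservative, and TTF carries no test. All of this stands and limits the severity. It does not defend the rule, which has no offsetting benefit.

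A second reply is that section 3.2.5 gives no dating rule for a PD failure, and section 7.2.5 analyses TTF by IRRC and by investigator separately, so PD failures might be dated at the scan. That is fair, and the assumed lag has no source in the documents. With zero lag the bias shrinks: at a 6-month minimum with 12-month accrual, from 2.4–5.1 points to 0.6–2.4. It does not vanish, because toxicity stops and deaths still fall between scans.

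Two stronger readings are tempting. A reader might infer that every ongoing subject loses 2 to 6 months. Those figures are the intervals between scans, and the gap can be as short as zero. A reader might also infer that the 6-month FL Primary Analysis is affected, but Table 4 does not list TTF there.

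**Conclusion.** The rule is wrong as written, and its effect is minor. Mechanism and direction follow from section 3.2.5, together with the inference that failures count up to the cutoff. SAP 1.2 and the absence of any limit support that inference, although the TTF section does not say so in words.

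At about 14 months' minimum follow-up, which is the current protocol's MZL trigger and roughly the FL NDA Analysis, the median and 1-year rate are essentially sound. The tail of the plot is about 1 to 2 points too low at 18 months and 2 to 12 at 24 months. If the SAP's 6-month MZL Primary Analysis is run as written, the 1-year rate is about 1 to 5 points too low and the median about 0.1 to 3 months too short. All sizes rest on the assumed accrual, hazards and lag.

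A reader might conclude that TTF is materially understated throughout. The documents do not support that: the early curve is essentially unaffected, and the larger figures belong to a 6-month MZL trigger that only the SAP, last updated for Amendment 4, still carries. The primary ORR analysis is unaffected.

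**What to change.** Replace the first TTF censoring bullet in SAP 3.2.5 with: *Subjects who are alive and on treatment at the data cutoff are censored at the data cutoff date.* This matches section 3.3.3.

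Do not add a fallback to the last date known on treatment. After Cycle 7, visits are every three cycles (Protocol 8.5). If that date were read as the last visit, a gap of up to about 3 × 28 = 84 days would return.

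The cost is one sentence and a small programming change, with no new data, since SAP 8.1 already uses on-treatment status at the cutoff.

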### **3.2.6. Recapture of Response**

Recapture of response is defined as achieving a second documented CR or PR after experiencing the first PD. The CT scan at PD will be used as new baseline for assessing disease response to ME-401.

Recapture of response rate (RRR) is defined as the proportion of subjects who achieved a CR or PR followed by a PD during IS dosing and subsequently switched to CS dosing and achieved a second documented CR or PR.

Time to recapture of response is defined as the time from the first PD until the second documented CR or PR. Subjects who do not have the second documented CR or PR will be censored at last time of response assessment.

### **3.2.7. Overall Survival (OS)**

OS is defined as time from date of first dose of study drug until death from any cause. OS will be censored at the last date the subject is known to be alive when the confirmation of death is absent or unknown.

## **3.3. Safety Endpoints**

### **3.3.1. Overall Incidence Rate of Treatment-Emergent Adverse Events (TEAEs)**

A TEAE is defined as any new or worsening adverse event occurred after first dose of study drug until 30 days after last dose of ME-401.

The overall incidence rate of TEAEs is calculated as the proportion of subjects with at least one TEAE.

The overall incidence rate of serious adverse events (SAEs) will also be calculated.

### **3.3.2. Incidence Rate of Adverse Event of Special Interests (AESIs)**

The rate of AESIs is calculated as the proportion of subjects with at least one AESI.

### **3.3.3. Time to Occurrence of Adverse Event of Special Interests (AESIs)**

Time to occurrence of AESIs is defined as the time from first dose of study drug to first occurrence of an AESI.

Censoring rules for time to occurrence of AESIs:

- Subjects without AESI who are still on treatment will be censored at the data cutoff date;
- Subjects without AESI who discontinue from treatment will be censored at the treatment discontinuation date.

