- k. **Hepatitis B and C testing** – Hepatitis B core antibody, Hepatitis B surface antigen, and hepatitis C antibody are required. Hepatitis B PCR is required if hepatitis B core antibody and/or surface antigen is positive. Hepatitis C PCR is required if hepatitis C antibody is positive.
- l. **Adverse events** – Recorded from the time of the first dose of study drug on Cycle 1 Day 1 and continues until 30 days after the last dose of study drug or start of new anti-cancer treatment.
- m. **Concomitant medications** – Recorded from 28 days prior to Cycle 1 Day 1 until the EOT/30-Day Safety Follow-up visit, or start of new anti-cancer treatment. Please, record information about COVID-19 vaccination, if performed.

- n. **ECG** – 12-lead ECGs performed at screening; Cycle 1 Day 1 pre-dose (unless the Screening visit is within 3 days prior to Day 1); pre-dose on Day 1 of Cycles 3, 6, 13, 19, and 25, and every 6 months thereafter; at the EOT/30-Day Safety Follow-up visit, and as clinically indicated. ECGs should be performed pre-dose. For Cycle 1 Day 1 and Cycle 3 Day 1, ECGs should be taken pre-dose and at expected  $C_{max}$  (3–5 hours after dosing).
- o. **CBC with differential** – WBC, ANC, RBC, HGB, HcT, lymphocytes, eosinophils, monocytes, basophils, platelets, and MCH. Screening labs must be repeated if performed >7 days prior to Cycle 1 Day 1.
- p. **Serum chemistry** – Glucose, BUN or urea, creatinine, sodium, potassium, chloride, calcium, ALP, AST, ALT, total bilirubin, total protein, albumin, LDH, and phosphorous. Screening labs must be repeated if performed >7 days prior to Cycle 1 Day 1.
- q. **Coagulation** – aPTT, PT/INR. Screening labs must be repeated if performed >7 days prior to Cycle 1 Day 1.
- r. **Urinalysis** – Dipstick or urine test (pH, specific gravity, glucose, ketones, blood, and protein). Screening labs must be repeated if performed >7 days prior to Cycle 1 Day 1.
- s. **COVID-19 test results** – Please record COVID-19 test results in the AE CRF page, if positive.
- t. **Issue and Assess Compliance Diary** – Compliance diary to record daily study drug administration. Returned diaries are to be assessed for study product compliance. New compliance diary is to be issued with each dispensing of ME-401.

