### **8.3. Adverse Events and Adverse Events of Special Interest**

Adverse events (AEs) will be captured from the first dose of study drug and continue until 30 days after the last dose of study drug. All AEs will be classified to SOC and PT by MedDRA Version 21.1 or later.

The Investigator will assess AEs for severity and relationship to study drug and determine if an AE meets the criteria for a SAE. The relationship of an AE to study drug is to be classified as ‘Related’, ‘Possibly Related’, or ‘Not Related’ by investigators. The study drug related AEs include both ‘Related’ and ‘Possibly Related’ AEs. Each AE will be graded using National Cancer Institute Common Terminology Criteria for Adverse Events (NCI CTCAE) v5.0. For the purpose of the summaries, AEs with missing relatedness will be considered to be related ME-401. AEs with missing severity (CTCAE grade) will be considered grade 3 (severe).

All AE listings will include the date of onset, date of resolution (if AE is resolved) and investigator’s assessment of severity and relationship to study drug. Missing (partial) start/stop dates will appear as missing (partial) in the subject data listings, but will be imputed to permit proper tabulation of AE data (See [Section 5.3.1](#)).

AEs will be summarized descriptively by number and percentage (%) of subjects with an event (n (%)), and number of events [e], by MedDRA SOC/PT and CTCAE grade.

A subject will be counted once at the SOC level and once at PT level. For summaries by SOC, PT, and intensity, a subject will be counted only at the maximum intensity level. Summaries by relatedness would be handled similarly to the summaries by intensity. Summaries by SOC and PT will be ordered by overall descending frequency of SOC and then, within a SOC, by overall descending frequency of PT. Summaries of PT will be ordered in descending frequency of PT.

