#### **8.3.1. Treatment-Emergent Adverse Event (TEAE)**

TEAE is any new or worsening AE that started after the first dose of study drug until 30 days after the last dose of study drug. Treatment emergence will be determined by comparing the AE onset date with first dose date. If AE onset date is incomplete, treatment emergence will be imputed according to the algorithm in [Section 5.3.1](#). In general, only TEAEs will be included in the AE summaries but all AEs will be included in the listings.

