### **8.3.3. Summaries of Incidence of Adverse Events**

The number and percentage of subjects reporting TEAEs and AESIs will be summarized as below:

- Overall summary of TEAEs and AESIs
- TEAEs by SOC and PT
- TEAEs by PT
- TEAEs of Grade 3 and above by PT
- TEAEs by maximum grade and PT
- TEAEs leading to treatment discontinuation by PT
- TEAEs related to ME-401 leading to treatment discontinuation by PT
- TEAEs leading to treatment interruption by PT
- TEAEs related to study drug by PT
- AEs leading to death by PT
- Treatment-related AEs leading to death by PT
- Treatment-Emergent SAEs by SOC and PT
- Treatment-Emergent SAEs by PT
- Treatment-Emergent SAEs by maximum grade and PT
- Treatment-emergent AESIs by AESI Type and PT
- Treatment-emergent Grade 3 and Above AESIs by AESI type and PT
- Covid-19 events by grade
- Other important safety events including opportunistic infection, CMV infection, PJP infection, and fungal infection, cytopenia event, pulmonary event by maximum grade and PT

Selected analysis on TEAEs will be summarized by subgroups.

Listings will be produced for all AEs, TEAEs, SAEs, AEs leading to treatment discontinuation, AEs leading to death, AESI, and for subjects with grade 3 and above AEs.

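### Time to AESI counts events up to 30 days after the last dose but censors event-free subjects at an undefined discontinuation date, so the Kaplan-Meier curve can be biased upward

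*SAP*

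**What the plan says.** SAP 3.3.3 gives the endpoint with no restriction to on-treatment events: "Time to occurrence of AESIs is defined as the time from first dose of study drug to first occurrence of an AESI". It has two censoring rules. For subjects on drug: "Subjects without AESI who are still on treatment will be censored at the data cutoff date". For subjects off drug: "Subjects without AESI who discontinue from treatment will be censored at the treatment discontinuation date".

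The event window comes from other sections. SAP 3.3.1 defines a TEAE as "any new or worsening adverse event occurred after first dose of study drug until 30 days after last dose of ME-401". SAP 8.3 says that AEs "will be captured from the first dose of study drug and continue until 30 days after the last dose of study drug", and a footnote to the Schedule of Assessments (SAP Table 1) says that recording "continues until 30 days after the last dose of study drug or start of new anti-cancer treatment". SAP 8.3.1 adds: "In general, only TEAEs will be included in the AE summaries but all AEs will be included in the listings". SAP 8.3.3 lists the AESI table as "Treatment-emergent AESIs by AESI Type and PT".

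SAP 8.3.4 asks for the Kaplan-Meier median with its confidence interval, the numbers of events and censored subjects, and figures, all by dosing group, plus the same analysis for Grade >=3 AESIs. It adds no censoring rule. Protocol 11.2.2 says only that Kaplan-Meier methods will be used. The SAP does not define the treatment discontinuation date; Table 1 names last dose and treatment discontinuation as alternative anchors for the end-of-treatment visit.

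**The concern.** Take two subjects who stop on the same day. One has an AESI 20 days after the last dose, within the capture window, and counts as an event on that day. The other has no AESI by the end-of-treatment visit, about 30 days after the last dose, where new AEs are reviewed (Protocol 8.6). The second subject was observed just as long, yet under the stated rule leaves the risk set at discontinuation. Whether a subject stays at risk after stopping is then decided by what happens next, which Kaplan-Meier estimation does not allow.

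Time to AESI is a listed secondary endpoint, and the protocol's rationale for the intermittent schedule (IS) includes a display of time to Grade 3 AESI under the two schedules (Protocol 2.3, Figure 4). The curves here will also be shown by dosing group. If the groups discontinue at different rates, the artefact differs between the curves.

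**Working it through.** **The plan's own figures.** Neither document states a Kaplan-Meier AESI incidence, so there is none to reproduce. The AESI precision statements in SAP 2.4 do reproduce with Clopper-Pearson limits: 15/120 = 12.5% (7.2-19.8) and 25/184 = 13.6% (9.0-19.4). They are crude proportions, which the censoring rule does not touch.

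**Direction.** Compare the SAP rule with an aligned rule that censors event-free discontinued subjects at the earlier of last dose + 30 days and data cutoff. Events and event times are identical. Each Kaplan-Meier factor is 1 - d/n, with the same d. If discontinuation is recorded no later than last dose + 30 days, n under the SAP rule is never larger. Estimated incidence is therefore never lower, and it is higher once any AESI occurs while a prematurely removed subject should still be at risk. The simulation below found no exception in any scenario.

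**Inputs for size.**
- N = 120, and 12.5% as an illustrative 12-month Grade >=3 risk (SAP 2.4).
- Any-AESI 12-month risk of 40%: assumption.
- Discontinuation: Phase 1b IS, 13 of 43 with median follow-up 155 days (Protocol 1.6.2.3), giving -ln(1 - 13/43)/155 = 0.00232 per day; or a slower 30% per year (assumption), -ln(0.7)/365 = 0.00098 per day.
- Hazard after stopping 1, 2 or 3 times the on-treatment hazard: assumption.
- Uncovered gap: 30 days if the recorded date is the last dose date; 30 - 21 = 9 days if it is 21 days later (IS off-drug period, SAP 2.3).
- Exponential times, cutoff uniform over 6-24 months, 2,000 replicates.

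**12-month incidence, SAP rule vs aligned rule (%), for post-stop hazard 1x / 2x / 3x.**

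| AESI | Discontinuation | Gap (days) | 1x | 2x | 3x | Excess (points) |
|---|---|---|---|---|---|---|
| Grade >=3 | Phase 1b IS | 30 | 13.4 vs 12.6 | 14.2 vs 13.3 | 14.9 vs 14.1 | 0.8-0.9 |
| Grade >=3 | 30%/year | 30 | 12.9 vs 12.5 | 13.2 vs 12.8 | 13.5 vs 13.2 | 0.3-0.4 |
| Any | Phase 1b IS | 30 | 42.1 vs 40.0 | 44.0 vs 42.0 | 45.7 vs 43.8 | 1.9-2.1 |
| Any | 30%/year | 30 | 40.9 vs 40.0 | 41.7 vs 40.9 | 42.4 vs 41.6 | 0.8-0.9 |
| Grade >=3 | Phase 1b IS | 9 | 12.8 vs 12.6 | 13.1 vs 12.8 | 13.3 vs 13.1 | 0.2-0.3 |
| Grade >=3 | 30%/year | 9 | 12.7 vs 12.5 | 12.7 vs 12.6 | 12.9 vs 12.8 | 0.1-0.2 |
| Any | Phase 1b IS | 9 | 40.7 vs 40.1 | 41.3 vs 40.7 | 41.9 vs 41.3 | 0.6 |
| Any | 30%/year | 9 | 40.3 vs 40.0 | 40.6 vs 40.3 | 40.8 vs 40.6 | 0.2-0.3 |

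**Hand check at 1x.** With discontinuation hazard m and gap g, the aligned risk set is about exp(m x g) times the SAP risk set, so the cumulative hazard H is inflated by about that factor. For Phase 1b IS discontinuation and g = 30, the factor is exp(0.00232 x 30) = 1.072.
- Grade >=3: H = -ln(0.875) = 0.1335; x 1.072 = 0.1432; 1 - exp(-0.1432) = 13.3%, an excess of 0.8 points over 12.5%.
- Any AESI: H = -ln(0.60) = 0.5108; x 1.072 = 0.5477; 1 - exp(-0.5477) = 42.2%, an excess of 2.2 points over 40%.
- With g = 9 the factor is 1.021 and the excesses are about 0.2 and 0.6 points.

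These agree with the simulation to about 0.1 point.

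**The case against.** **The direction is conditional.** Censoring is tied to treatment discontinuation, the event window to the last dose. On the IS a stop recorded at a Day 1 visit is already about 21 days after the last dose, and an interruption may last 6 weeks before permanent discontinuation (Protocol 5.3.1). A date at last dose + 30 days removes the bias. A later date, with events cut off at 30 days, could reverse it. This stands: a reader might infer that the curve must be too high, but the documents do not fix the date.

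**The 12-month incidence is not a listed output.** SAP 8.3.4 lists medians, counts and figures. In every scenario above the curve is below 50% at 12 months under both rules, so no median is reached by then, and event and censoring counts do not change. This stands. The 12-month figures measure the shift in the plotted curve; they are not an error in a planned table entry.

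**The effect is small.** The SAP's own interval for 15/120 is 19.8 - 7.2 = 12.6 points wide. AE recording also ends at new anti-cancer treatment, and 9 of 13 Phase 1b IS discontinuations were for progression (Protocol 1.6.2.3), so the uncovered window may often be shorter than 30 days. The simulation does not model this, so its 30-day rows are towards the upper end.

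**The rule might imply on-treatment events only.** The text does not say so: the censoring rule covers only subjects without an AESI, and a subject with an event on day 20 after the last dose is not one. If that was the intent, it should be written, and the Kaplan-Meier event count could then differ from the treatment-emergent AESI table.

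**Two stronger readings fail.** A reader might infer a distorted formal comparison of schedules, but no test or contrast is specified; results are only presented by dosing group. A reader might also infer that the flaw strikes when delayed toxicities appear, but the protocol links those to continuous dosing (Protocol 1.6.2.3 and 2.3), not to the 30 days after stopping.

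**Conclusion.** The mismatch is real, and no passage resolves it. As written, the rule makes censoring depend on the later outcome and biases the time-to-AESI curve upward when discontinuation is recorded before last dose + 30 days. The 12-month excess is about 0.3-0.9 points (Grade >=3) or 0.8-2.1 points (any AESI) with the full 30 days uncovered, about 0.1-0.6 points with a 21-day lag, and nil at last dose + 30 days. These sizes rest on the assumed AESI, discontinuation and post-stop hazards, which the documents do not give for this trial.

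The consequence is confined to the descriptive curves and any medians. A reader might infer that the SAP 2.4 criterion for ruling out a Grade >=3 AESI rate of 20% is undermined; it is not, because that uses crude proportions. Efficacy is untouched. The point is worth correcting because it concerns a listed secondary safety endpoint and is cheap to repair.

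**What to change.** Replace the second censoring bullet in SAP 3.3.3 with wording such as: *Subjects without an AESI who have discontinued treatment are censored at the earliest of last dose + 30 days, start of new anti-cancer therapy, death, last contact or withdrawal of consent, and data cutoff.* Last contact and withdrawal are needed so that subjects no longer observed are not credited with event-free time.

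State in the same section that AESIs count as events only over that same window, and apply both sentences to the Grade >=3 analysis in SAP 8.3.4. If only on-treatment events are wanted instead, say so, define the treatment discontinuation date, and count AESIs only up to it.

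The cost is a sentence or two in the SAP and a small programming change, with no new data collection. The change does not address death or toxicity- and progression-driven stopping as competing or informative events; that is a separate question.
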